Allograft are equivalent to historical high level published data of similar product (Data reported in Meta-analysis ACDF obtained from FDA disc arthroplasty trials).

This White Paper research on new Biologic Platform (BIO⁴ Viable Bone Matrix) will enroll 20 patients. The study with the current sample size tends to serve as an exploratory pathway to another higher Level 1 study with a similar study design. Characteristics of subjects and clinical variables will be analyzed using means and standard deviations calculations. Independent t-tests will be used to compare the means of continuous variables. The normally distributed data will be presented as mean \pm standard deviation. The non-normally distributed data will be expressed as medians (interquartile range) and will be analyzed via the Mann-Whitney's U test. Descriptive variables will be subjected to χ^2 analysis or Fisher's exact test as appropriate. The level of significance will be set at $\alpha=0.05$. SPSS 14.0 for windows statistical software will be used for this study.

4. Procedures

This is a prospective study with the intent to investigate the efficacy of BIO⁴ bone matrix in patients undergoing 1 or 2-level ACDF spine surgery. At the time a patient is scheduled for surgery, the patient's chart will be evaluated for inclusion/exclusion criteria. If a patient meets the criteria for the study, the study will be explained to the patient and consent obtained.

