In addition to the basic demographics (age, gender, BMI, smoking status) and operative details (operative time, total blood loss, time of ambulation and perioperative complications), the study aims to collect the data for the following: 1) radiological assessment of fusion (cervical spine x-ray and if needed, CT at 1 year follow up) as the primary endpoint; 2) Arthrodesis rates assessed using CT (1 year follow up, if needed) and AP, lateral, dynamic flexion-extension cervical spine x-rays pre-op, post-op 2~4 weeks (no flexion-extension) (10~34 days post op), 3 months (83~97 days post op), 6 months (173~187 days post op) and 1 year (primary data point outcome) (351~379 days post op); 3) revision rates (if any); 4) outcome scores (Visual Analog Scale, VAS and Neck Disability Index, NDI) pre-op, post-op 2 ~ 4 weeks, 3 months, 6 months and 1 year.

6. Participants

a. Target population

20 individuals who are skeletally mature with cervical pain would be considered as potential subjects for the study.

b. Inclusion Criteria:

- Ages 18 -75 years
- Scheduled 1 or 2-level ACDF spine surgery
- The capacity to provide informed consent.
- Subject has one or more of the following diagnoses:
 - i) Degenerative Disc Disease (as defined by neck pain of discogenic origin with degeneration of the disc confirmed by patient history and radiographic studies)
 - ii) Trauma (including fractures)
 - iii) Tumors
 - iv) Deformities or curvatures (including kyphosis, lordosis, or scoliosis)

- v) Pseudoarthrosis
- vi) Failed previous fusion
- vii) Decompression of the spinal cord following total or partial cervical vertebrectomy
- viii) Spondylolisthesis
- ix) Spinal stenosis

c. Exclusion Criteria

Patients with any of the following conditions will be excluded, or if enrolled and found to be ineligible and do not fit the inclusion criteria, will be withdrawn from the study.

- Patients with current or recent history of malignancy or infectious disease.
- The inability to provide informed consent.
- Subject has marked local inflammation
- Subject has any mental or neuromuscular disorder which would create an unacceptable risk of fixation failure or complications in postoperative care.
- Subject has a bone stock compromised by disease, infection or prior implantation which cannot provide adequate support and/or fixation to the devices.
- Subject has bone abnormalities preventing safe screw fixation.
- Subject has any open wounds.

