- Subject has rapid joint disease, bone absorption, osteopenia, osteomalacia, and/or osteoporosis. Osteoporosis or osteopenia are relative contraindications, since this condition may limit the degree of obtainable correction and/or the amount of mechanical fixation.
- Subject has a documented or suspected metal sensitivity.
- Subject is pregnant.
- Subject has anatomical structures or physiological performance that would interfere with implant utilization.
- Subject has inadequate tissue coverage over the operative site.
- Subject has other medical or surgical conditions which would preclude the potential benefit of surgery, such as congenital abnormalities, immunosuppressive disease, elevation of sedimentation rate unexplained by other diseases, elevation of white blood count (WBC), or marked left shift in the WBC differential count.
- Note: The Aviator Anterior Cervical Plating System is not approved or intended for screw attachment to the posterior elements (pedicles) of the cervical, thoracic, or lumbar spine. The surgeon must consider the levels of implantation, patient weight, patient activity level, and other patient conditions which may impact on the performance of the system.

d. Benefits

There are no direct benefits to patients from being in this study. Information gathered in this study may benefit others who undergo this procedure in the future. Long term, studies

like this may help clinicians better understand the benefits of doing spine surgery with BIO⁴ bone graft, BIO AVS cervical allograft and Aviator anterior cervical plating system.

e. Risks

All procedures will be performed by the Board Certificate Orthopedic Surgeons (principal and co-investigators) who have performed several such procedures in the past. The only risks that patients would be subjected to are same that are associated with any such procedures. There may be potential cancer risks associated with similar bone graft products. All the patients will be followed up closely post-operatively for any risks and treated accordingly. There may be confidentiality risks associated with the study. All efforts will be made to minimize this risk.

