collection sheet. The forms will be filed in the patient binder. Clinical and demographic data will be captured from the medical record and mentioned in the data collection sheet. These data will be collected at Seton Spine and Scoliosis Center. Specifically, in addition to the basic demographics (age, gender, BMI, smoking status) and operative details (operative time, total blood loss, time of ambulation and perioperative complications), the study aims to collect the data for the following: 1) radiological assessment of fusion (cervical spine x-ray and if needed, CT at 1 year follow up) as the primary endpoint; 2) Arthrodesis rates assessed using CT (1 year follow up, if needed) and AP, lateral, dynamic flexion-extension cervical spine x-rays pre-op, post-op 2~4 weeks (no flexion-extension), 3 months, 6 months and 1 year (primary data point outcome); 3) revision rates (if any); 4) outcome scores (VAS and NDI) pre-op, post-op 2 ~ 4 weeks, 3 months, 6 months and 1 year.

b. The data collection sheet will not have any personal information of subjects (such as date of birth, SSN, etc.). Despite this, all the study documents will be stored locked in a locked office at the Spine Center. The initial data sheet will have a coded number on it, and this coded number will be used to collect follow-up study related information. Only the principal/co-investigators and the study coordinator will have access to the documents. The electronic data sheet will be stored on investigators and study coordinator's Seton computers which are password protected.

c. The study data will be kept for 2 years from the conclusion of the study.

d. Study participants will be assigned a study number, and their data coded and de-identified in the data bases. All efforts will be made to protect the privacy of subjects and maintain confidentiality of data collected. The data collection sheet will not have any personal information of subjects (such as date of birth, SSN, etc.). Despite this, all the study documents will be stored locked in a locked office at the Spine Center. The initial data sheet will have a coded number on it, and this coded number will be used to collect follow-up study related information. Only the principal/co-investigators and the study coordinator will have access to the confidential documents. These confidential documents will not be shared by other researchers for research purposes.

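### The data lists have no item for complications after an undefined perioperative period, other than revisions, although study visits run to 1 year

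*Combined protocol and SAP*

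**What the plan says.** Section 5 (Measures) lists what the study aims to collect, and Section 7a (Privacy and Confidentiality) repeats the list. Both contain demographics, operative details, radiographic fusion, revisions, and VAS and NDI scores.

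- **Early harm.** Complications appear only among the "operative details (operative time, total blood loss, time of ambulation and perioperative complications". The documents do not say how long the perioperative period lasts.
- **Later harm.** The only later event listed is "3) revision rates (if any". Section 7a adds nothing: "3) revision rates (if any); 4) outcome scores (VAS and NDI) pre-op, post-op 2 ~ 4 weeks, 3 months, 6 months and 1 year".
- **Follow-up.** Section 5 places the last visit at "1 year (primary data point outcome) (351~379 days post op", after visits at 2-4 weeks, 3 months and 6 months.
- **Risks.** Section 6e states: "There may be potential cancer risks associated with similar bone graft products". It then says: "All the patients will be followed up closely post-operatively for any risks and treated accordingly".
- **Data source.** Section 7a says: "Clinical and demographic data will be captured from the medical record and mentioned in the data collection sheet".
- **Size.** Section 3 says the study "will enroll 20 patients" and presents it as an exploratory step towards a larger study of similar design.

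The documents contain no adverse-event definition, collection period, reporting route or safety summary.

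**The concern.** Patients are seen for a year, but the listed safety data are tied to the operation, apart from revisions. A late complication treated without revision has no place in either list. What is not asked for in the same way at the 3-, 6- and 12-month visits cannot be reliably reconstructed at analysis. Section 7e also provides for the code and research records to be destroyed after the final analysis, which would close off later linkage to patients.

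At stake is how a blank can be read. The title and the hypothesis in Section 3 both refer to clinical as well as radiographic outcomes, so a reader of the report will want to know what happened to patients between surgery and 1 year. If no late complication other than revision is reported, that reader cannot tell whether none occurred or none was sought. Because the planned larger study would have a similar design, the same list could be carried forward into it.

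**Working it through.** The plan gives no safety figure to reproduce: there is no expected event rate, power statement or precision target for harm. The check is a comparison of the text, followed by arithmetic for scale.

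**1. Text comparison**

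| Late event | Item in the Section 5 and 7a lists |
|---|---|
| Revision | Yes |
| Non-fusion | Yes, by imaging |
| Worse pain or disability | Yes, VAS and NDI, but without a cause |
| Infection, graft reaction or new neurological deficit, managed without revision | None |
| New malignancy | None |
| Stop of participation for health reasons (allowed in Section 6e) | None for the underlying event |

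The Section 6e sentence on follow-up concerns care and does not mention recording. The Section 7a sentence on the medical record looks broader, but the sentence after it spells out the content and returns to the same list.

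**2. Share of follow-up affected**

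Inputs: 1 year = 365 days. The length of the perioperative period is an assumption, taken as 30 to 90 days.

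- 30 days: (365 - 30)/365 = 335/365 = 92%
- 90 days: (365 - 90)/365 = 275/365 = 75%

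Using the edges of the last visit window from Section 5 changes little:

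- Day 351: 321/351 = 91% and 261/351 = 74%
- Day 379: 349/379 = 92% and 289/379 = 76%

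These shares apply to events other than revision, since revisions are listed without a time limit.

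**3. What 20 patients could show with full capture**

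Input: n = 20 (Section 3). The event rates are assumptions, because the documents give none.

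Probability of at least one event = 1 - (1 - p)^20:

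| Assumed 1-year rate p | Probability of at least one event |
|---|---|
| 0.1% | 2.0% |
| 1% | 18.2% |
| 5% | 64.2% |
| 10% | 87.8% |

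Upper limit of the exact two-sided 95% interval for 0/20 = 1 - 0.025^(1/20) = 16.8%.

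A late complication with a true rate of 5% to 10% would therefore more likely than not occur at least once in this cohort, with no item to record it. A rare event would probably not be seen at all, and a zero count would exclude only rates above 16.8%.

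**The case against.** The strongest reply is that this is a small exploratory efficacy series with no safety endpoint, hypothesis or claim, using a product on label that patients can also receive outside the study. The lists are introduced as what the study aims to collect and are not declared exhaustive. Clinic staff have access to the medical record, and the data collection sheet itself is not in the documents. Revisions, imaging and VAS/NDI would show some late harm. No primary-endpoint result changes.

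Much of this stands, and it limits what can be said. Three stronger readings are tempting:

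- **That late harm would go entirely unrecorded.** A reader might infer this from the lists. The documents do not support it: revisions are listed, some harm would show indirectly through imaging or scores, and the sheet has not been seen. The supportable statement is that no explicit provision is made.
- **That patients are not watched for late harm.** Section 6e says that they are. What is missing is the link from that care to the study data.
- **That the trial ignores a known cancer risk of its own product.** Section 6e attributes the possible risk to similar graft products, not to BIO⁴. At an assumed rate of 0.1%, the chance of seeing even one case in 20 patients is about 2%, so better recording would not let this study assess it.

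The reply does not remove the core. Access to records is not systematic questioning at fixed visits, a worse NDI score does not identify an infection or a deficit, and the only detailed statement of content in Section 7a repeats the same list.

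**Conclusion.** The point holds as a gap in data collection. As written, the plan has no item for complications after the perioperative period other than revisions, and does not say when that period ends. For those events the gap covers about 75% to 92% of the year, assuming a perioperative window of 90 to 30 days; the documents support no single value in that range.

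The ground for the point is late complications managed without revision. It does not rest on the cancer statement, and the primary fusion endpoint is unaffected. Even with full capture the safety data would be descriptive, as the 16.8% limit for 0/20 shows. The change is still worth making: it alters what is collected, it cannot be reliably made good at analysis, and it uses visits that already take place.

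**What to change.** Amend the lists in Sections 5 and 7a, keeping them identical:

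1. Give perioperative complications a stated time window for data recording.
2. Add an adverse-event item to the data collection sheet at the existing 2-4 week, 3-, 6- and 12-month visits, covering the time since the previous visit. Record event type, onset date and seriousness, with an explicit entry for no event so that a blank cannot be taken as none. The types should include infection, graft reaction, new neurological deficit and new malignancy. Cross-refer revisions so that they are not counted twice.
3. State in the analysis text of Section 3 that the number and percentage of patients with any event will be reported with an exact 95% interval, as description only.

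The cost is a short amendment, one more section on the sheet, and a little coordinator and investigator time, the latter mainly for judging seriousness. No extra visits, tests or patients are needed, and clinical management does not change.

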Subject's participation in this research is voluntary and will be allowed to discontinue from the study anytime he/she wishes to. If the subject choose not to participate, it will not affect his/her relationship with the study doctors or the study doctor's institution, or their right to health care or other services to which they are otherwise entitled at our center. Subject's participation may be stopped by the PI/Co-PI under the following or other circumstances: (1) to protect subject's health and safety, (2) because the subject fails to come in for his/her scheduled study visit, or (3) the study is stopped for any reason.

f. Recruitment

Subjects will be recruited from the Seton Spine & Scoliosis Center, Austin, TX. Recruitment will continue until 20 subjects are enrolled and scheduled with 1 or 2-level ACDF spine surgery at levels C2-T1.

g. Obtaining Informed Consent

The inclusion and exclusion criteria check list will be completed and consent obtained in private in a clinical setting at Seton Spine and Scoliosis Center. After the initial evaluations by investigators, they will address enrollment in the prospective study with his/her patient. Potential subjects will be educated about all essential aspects of the study including the requirements for enrollment, the study procedures, and all risks and benefits of participation. Potential subjects will be given the opportunity to ask questions. After questions have been answered, potential subjects that are interested in enrolling in the study will be asked to sign an informed consent. A copy of the signed informed consent documents will be given to the patient. In the event that a potential subject wishes to deliberate, shows any hesitation, or is not able to decide whether they will participate, the issue of enrollment will be deferred.

7. Privacy and Confidentiality

a. All the required study data will be collected by the study personnel at various study visits. All study personnel are the employed by the clinic and will have access to the patient medical records. During the patient visit, the outcome data such VAS and NDI will be collected on the VAS and NDI forms and scored will be transferred to the data

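### The protocol names no reader, no masking and no fusion definition for the primary endpoint, so an unmasked reading by the patient's own surgeon is allowed and likely

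*Combined protocol and SAP*

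**What the plan says.** **Endpoint.** Section 5 (Measures), repeated in Section 7a, lists "radiological assessment of fusion (cervical spine x-ray and if needed, CT at 1 year follow up) as the primary endpoint". The next item is "Arthrodesis rates assessed using CT (1 year follow up, if needed", together with plain and flexion-extension x-rays. Neither section says who reads the images, how many readers there are, what counts as fused, what makes a CT needed, or how a doubtful reading is settled.

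**Who operates.** Section 6e: "All procedures will be performed by the Board Certificate Orthopedic Surgeons (principal and co-investigators".

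**Who collects and sees the data.** Section 7a: "All the required study data will be collected by the study personnel at various study visits", and "All study personnel are the employed by the clinic and will have access to the patient medical records". The fusion assessment is in the list of data that Section 7a then gives. VAS and NDI forms go into the patient binder and their scores onto the data collection sheet. Section 7a also says "Clinical and demographic data will be captured from the medical record". Section 7b adds "Only the principal/co-investigators and the study coordinator will have access to the documents", and Section 7d "These confidential documents will not be shared by other researchers for research purposes". Study codes appear in 7b and 7d only as a privacy measure.

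**How the result is used.** Section 3 (Purpose) plans 20 patients, all given BIO4, compared with published historical data. It states no expected fusion rate and no margin.

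**The concern.** Without a written definition, deciding whether a level has fused is a judgement, and doubtful images can go either way. The protocol's only named holders of study documents are the people who placed the graft and a coordinator. Nothing stops the reader being the patient's own surgeon, and nothing keeps pain and disability scores or the clinical course away from that reader. A patient who is doing well may then be called fused on a film that would otherwise be left in doubt.

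The study has no concurrent group read under the same rules. Any leniency therefore enters directly into the one proportion that is compared with published rates. Section 3 presents the study as a step towards a Level 1 study of similar design, so an inflated rate could carry into the planning of that study.

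**Working it through.** The protocol gives no fusion rate, margin or power, so there is no planned figure to reproduce. The check has two parts.

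**1. What the text supports**

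| Question | Answer in the protocol |
|---|---|
| Who operates? | Principal and co-investigators (6e) |
| Who collects the data? | Study personnel, all clinic employees with chart access (7a) |
| Who sees study documents? | Investigators and coordinator only (7b); no sharing for research (7d) |
| Who reads the films? | Not stated |
| Is the reader masked to symptoms, VAS/NDI or notes? | Not stated |
| What is fusion, and when is CT needed? | Not stated |

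The first three rows make an investigator-surgeon the likeliest reader. The last three contain nothing that prevents it.

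**2. How much it could matter**

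Input from the protocol: N = 20. Assumptions: one fusion call per patient, and all 20 read at 1 year.

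- One doubtful case: 1/20 = 5 percentage points. One to four doubtful cases: 5 to 20 points.
- Assumed split of 16 clear fusions, 1 clear non-union and 3 equivocal cases, with x-ray alone deciding: strict 16/20 = 80%, lenient (16 + 3)/20 = 95%, a spread of 15 points.
- Exact (Clopper-Pearson) 95% intervals: 16/20, 56.3% to 94.3%; 19/20, 75.1% to 99.9%.

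To see the effect on the reported result, let p be the true fusion rate and q the share of non-fused cases called fused. Both are assumptions. Errors are taken to run in this direction only.

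- Rate called fused: r = p + (1 − p)q. Example: 0.80 + 0.20 × 0.25 = 0.85.
- Chance of reporting at least 19 of 20 fused: 20 r^19 (1 − r) + r^20.

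| True rate p | r at q = 0.25 to 0.50 | Chance of ≥19/20, q = 0 | Chance of ≥19/20, q = 0.25 to 0.50 |
|---|---|---|---|
| 80% | 85% to 90% | 6.9% | 17.6% to 39.2% |
| 85% | 88.8% to 92.5% | 17.6% | 32.5% to 55.1% |
| 90% | 92.5% to 95% | 39.2% | 55.1% to 73.6% |

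These figures show how sensitive the result is to lenient reading. They do not show that lenient reading will occur.

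**The case against.** **The surgeons are not named as readers.** From Sections 6e, 7b and 7d a reader might infer that the rules make the operating surgeons the readers. They do not. The access rules concern study documents and do not mention films, and Section 7a lets clinical data come from the medical record, so a routine imaging report by someone else is not excluded. This stands, and it limits the point to what the plan permits and makes likely. It does not remove the gap: no such report is specified as the endpoint, held to a definition or masked to clinical information.

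**The spread does not come from the reader alone.** Flexion-extension films are taken, and CT is available at 1 year. CT on equivocal cases could shrink the 15 points. This stands, but since the protocol does not say when CT is needed, a lenient x-ray reading may itself lead to no CT.

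**Masking alone does not settle strict against lenient calls.** Correct. A masked reader with no definition could still call the same three cases either way, so the remedy must include a definition.

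**Sampling error is larger, and the study is exploratory.** The interval for 19/20 does contain 80%. But sampling error is visible in the interval, whereas reading bias shifts the whole interval unseen. Section 3 also states an efficacy aim, a hypothesis and a 0.05 significance level.

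**Three further inferences go too far.**
- That the product's company pays for the study: the protocol names a sponsor but gives no funding terms and does not say that the sponsor makes BIO4.
- That no later analysis could repair the reading: a masked re-read before the final analysis is not ruled out, and Section 7c keeps study data for 2 years after the study ends.
- That the comparison with published rates must be biased upwards: this depends on how those films were read, which the documents do not say.

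**Conclusion.** The point holds as a gap in the primary endpoint: reader, masking and fusion definition are all unspecified, and the staffing and access rules make an unmasked reading by the patient's own surgeon possible and likely. It does not hold as a statement that the protocol assigns the reading to the surgeons, or that the result will be biased.

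Its size is 5 percentage points for each doubtful case at 20 patients. The 80% to 95% illustration rests on an assumed split of cases and on x-ray alone deciding. This is a change that should be made before any 1-year film is read. It is cheap, and it protects the only number that the primary endpoint yields.

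**What to change.** In Sections 5 and 7a, state that:

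- the endpoint reading at 1 year is made by a designated investigator who did not operate on that patient;
- the images carry only the existing study code and are read in shuffled order;
- the reader does not see VAS, NDI, symptoms or the surgeon's notes;
- the reading follows a radiographic definition of fusion written down before any 1-year film is read, including how a CT finding counts where a CT exists;
- the result is recorded on the data sheet before any discussion;
- the operating surgeon's clinical reading stays in the chart and is not the endpoint.

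Section 2 already lists a principal investigator and co-investigators, so no new staff and no change to the access rules are needed. If all of them take part in an operation, the protocol must say who reads for that patient.

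The cost is a few sentences of protocol text, coordinator time to relabel 20 sets of images and a few hours of an investigator's time. The reported fusion rate may come out lower. Masking remains incomplete: the reader is still a study investigator and knows that every patient received BIO4, so what is gained is separation from the surgeon and from the clinical outcome.
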